BPD	Bronchopulmonary Dysplasia
BPCA	Best Pharmaceuticals for Children Act
BW	Birth Weight
CA	Calcium
CFR	Code of Federal Regulations
CL	Clearance
C _{max}	Maximum Concentration
CRF	Case Report Form
DCC	Data Coordinating Center
DCF	Data Collection Form
DCRI	Duke Clinical Research Institute
DMC	Data Monitoring Committee
eCRF	Electronic Case Report Form
FiO ₂	Fraction of Inspired Oxygen
FDA	US Food and Drug Administration
GA	Gestational Age
GAS	Global Assessment Scale
GCP	Good Clinical Practice
GFS	Gel-forming solution
HIG	Hemangioma Investigator Group
HIPAA	Health Insurance Portability and Accountability Act
HR	Heart Rate
IB	Investigator's Brochure
ICF	Informed Consent Form
ICH	International Council for Harmonisation
ICMJE	International Committee of Medical Journal Editors
IDES	Internet Data Entry System
IEC	Independent or Institutional Ethics Committee
IH	Infantile Hemangioma

Abbreviation	Definition
IND	Investigational New Drug Application
IRB	Institutional Review Board
IV	Intravenous
K	Potassium
kg	Kilogram
L	Liter
MedDRA	Medical Dictionary for Regulatory Activities
mg	Milligram
mcg	Microgram
MOP	Manual of Procedures
N	Number (typically refers to participants)
Na	Sodium
ng/mL	Nanogram per milliliter
NICHD	Eunice Kennedy Shriver National Institute of Child Health and Human Development
NIH	National Institutes of Health
NRN	Neonatal Research Network
PI	Principal Investigator
PICU	Pediatric Intensive Care Unit
PNA	Postnatal age
PMA	Postmenstrual age (gestational age plus postnatal age)
PK	Pharmacokinetic
PTN	Pediatric Trials Network
PTN POP01	Pharmacokinetics of Understudied Drugs Administered to Children per Standard of Care
QOL	Quality of Life
RAD	Reactive airway disease
SAE	Serious Adverse Event
TOF	Tetralogy of Fallot
TORO	Transfer of Regulatory Obligations
$t_{1/2}$	Half-life
VAS	Visual Analog Scale
V _{ss}	Volume of distribution at steady state
WHO	World Health Organization

PROTOCOL SYNOPSIS

Protocol Title:	Efficacy, Safety and Pharmacokinetics of Topical Timolol in Infants with Infantile Hemangioma (IH)
Phase:	2
Product:	0.25% and 0.5% Timolol Maleate Gel Forming Solution (GFS) for topical application to IH
Objectives:	
Primary: Describe the efficacy of 0.25% and 0.5% topical timolol maleate GFS as assessed through IH changes in volume
 
Secondary: Describe the safety of topical timolol maleate GFS for treatment of IH
 
Exploratory: Describe the pharmacokinetics (PK) of topical timolol maleate GFS for treatment of IH

Study Design:	Multi-center, double-masked randomized, efficacy, safety, and PK study
Study Population:	
Inclusion Criteria
 
 1. Documented informed consent from legal guardian 2. 0-84 days postnatal age at time of first study dose or when enrolled into the non-intervention cohort. 3. Clinical diagnosis of superficial cutaneous or mucosal infantile hemangioma (must include all of the following): 
 a. Superficial lesion in the dermis b. Thin <2 mm in thickness c. ≥ 0.5 cm at its longest dimension and ≤ 10 cm² d. Involves skin or keratinized mucosa 
Exclusion Criteria
 
 1. History of previous treatment with any pharmacologic or laser therapy for IH 2. Ongoing therapy with an oral beta blocker or oral corticosteroid (e.g., cardiac arrhythmia, adrenal insufficiency, upper airway obstruction, tetralogy of fallot (TOF), hypertension, reactive airways disease) 3. IH that requires systemic therapy (defined by dynamic complication scale >3) 4. IH of the non-keratinized mucosa 5. Infants with more than one hemangioma that requires therapy 6. Hemodynamically significant cardiovascular disease, as determined by the investigator 7. Known allergy to beta blockers or vehicle 8. Heart rate <100 beats per minute at screening visit 9. Known prenatal or postnatal diagnosis of 2nd/3rd degree atrioventricular block 10. History of Reactive Airways Disease (RAD) 11. Any condition which would make the participant, in the opinion of the investigator, unsuitable for the study
Number of Participants:	Approximately 110
Number of Sites:	Approximately 10 sites

Duration of Participation:	Treatment arms: Up to 270 days (180 days of study drug plus 7 days of safety monitoring after last study dose for all adverse events and 90 days of safety monitoring after last study dose for adverse events of special interest). Non-Intervention cohort: Up to 180 days
Estimated Duration of study	Up to 2 years
Dose Schedule:	1:1 randomization to 0.25% versus 0.50% timolol GFS

2 BACKGROUND INFORMATION AND SCIENTIFIC RATIONALE

2.1 Background Information

The Best Pharmaceuticals for Children Act (BPCA) mandates the National Institutes of Health (NIH) prioritize therapeutic areas in critical need for pediatric labeling, sponsor pediatric clinical trials, and submit these data to the United States Food and Drug Administration (FDA) for consideration for labeling changes. This study will be conducted in accordance with Section 409I of the Public Health Service Act; as such, the results from this research may be submitted to the FDA for review and use in negotiated labeling changes. This research study is contractually supported by the Eunice Kennedy Shriver National Institute of Child Health and Human Development (NICHD). The NICHD awarded a contract to Duke University to establish the Pediatric Trials Network (PTN) through its Duke Clinical Research Institute (DCRI). The purpose of this contract is to facilitate trial design for studies supported by NIH. A separate contract was awarded to The Emmes Company to serve as the BPCA Data Coordinating Center (DCC).

Infantile hemangiomas (IH) are the most common tumor of childhood. In the United States, approximately 80,000 children per year are diagnosed with the tumor, 12-20% of which are significantly complex and require referral to specialists for consideration of treatment.

Complications of hemangiomas include permanent disfigurement, ulceration, bleeding, visual impairment, and airway obstruction. Hemangiomas occur exclusively in infants; therefore, efficacy, pharmacokinetic (PK), and toxicity data from older children and adults are not available. Furthermore, hemangiomas preferentially affect premature and low birth weight infants (<2500 g). According to a previous study, every 500 g reduction in birth weight below 2500 g results in a 25% increased risk of developing a hemangioma.¹

Efficacy of systemic beta-blockers for the treatment of IH has been reported. Historically, agents with reported activity in treating IH include corticosteroids, interferon alpha, and vinca alkaloids. In 2008, the initial report of oral propranolol use for the treatment of IH was published.² This was followed by a number of case series describing its efficacy for IH.³⁻⁹ Given propranolol's efficacy and immediate availability in a US suspension, it has rapidly been adopted as first-line therapy for IH.^{2,10} Furthermore, a multicenter, randomized, double-mask placebo-controlled, industry-sponsored trial of a new formulation of oral propranolol has been performed and this formulation was approved by the FDA for treatment of IH.¹⁰ In this study, 460 infants 1 to 5 months of age were randomized to either placebo or one of four dosing regimens. A rapid response to treatment was observed in 88% of infants receiving 3mg/kg/day by week 5.¹⁰

Despite its adoption as first-line systemic therapy for IH, the mechanism of action of oral propranolol for IH remains poorly understood. Investigators have proposed multiple mechanisms, including pericyte-mediated vasoconstriction, inhibition of vasculogenesis and catecholamine-induced angiogenesis, the disruption of hemodynamic force-induced cell survival, and the inactivation of the renin-angiotensin system.¹¹

Pediatric dermatologists are using topical timolol despite limited efficacy, safety, or pharmacokinetic data. The success of oral propranolol for IH treatment has led many practitioners to use topical beta blockers off-label for the treatment of IH.¹² There are currently no commercially available forms of propranolol designed for application to the skin; however, intraocular preparations of timolol are commercially available. Similar to the initial reports on oral beta blockers, publications on the use of 0.25% or 0.5% timolol maleate gel-forming intraocular solutions applied directly to hemangiomas on the skin or mucosa for off-label use in IH are rapidly emerging.

Efficacy of topical application of timolol for IH: Numerous case reports and small studies, including those of premature infants, have reported growth arrest and reduction in thickness and redness of IH within 2 weeks to 4 months topical application timolol maleate, particularly in superficial lesions.¹³⁻¹⁸ As a result, existing prospective studies of topical timolol for IH have focused on application to superficial IH rather than deeper lesions. In the largest available prospective study of 124 Chinese infants with IH, administration of timolol therapy directly to the IH for 4 months resulted in controlled growth of IH in 36/101 (36%) infants, and regression of IH in 56/101 (56%) infants. Only 3/23 (13%) infants in the control group had regression of IH.¹⁸ In a retrospective study, investigators treated 73 infants (median age 4.3 months, 25th, 75th percentiles: 2.6, 7.2 months) for a mean of 3.4 months, and the mean visual analogue scale improvement at the last follow-up visit was 45%.¹⁹ Previous investigators also conducted a prospective, placebo-controlled analysis of topical timolol efficacy in 41 infants, ages 5 to 24 weeks. Among those who received treatment, a higher proportion of IH decreased in size as assessed by the visual analog scale by >5% at week 20 compared to those who did not receive treatment, $p < 0.02$.²⁰ In a study of 25 infants treated for 6 months, timolol was more effective when applied to thinner, plaque-type morphology than nodular superficial lesions.¹⁷

Outcome scales used to assess efficacy of treatment for IH:

Because most of the growth observed in IH is in tumor thickness not width, assessment of IH progression or regression has proven difficult with standard methods of measurement. Therefore, investigators have developed several scales to assess IH growth and efficacy of treatment for IH. All available scales are based on a shared concept of visual changes (progression or regression) at the determined endpoint compared to baseline or time zero, and aim to convert subjective improvement or worsening to quantitative measures. The

[figure not shown]

Figure 1. IH on tip of nose, cheek and eyelid demonstrating 3 dimensional growth over 3 week period.

The visual analog scale (VAS) methodology is a widely accepted and frequently used measurement instrument for assessment of IH growth. When responding to a VAS item, raters specify the level of change from time zero to the endpoint (growth or regression) by indicating a position along a continuous line between two end-points. The best results are observed when lesional photographs are taken and a centralized assessment is made by unbiased, masked, and well-trained investigators. Although not formally validated, the VAS methodology has been used in several IH studies to evaluate response of IH to treatment with both topical and oral therapies. Most recently, a centralized VAS methodology was used in a study to gain FDA approval for an oral propranolol formulation for treatment of IH. Further, the VAS has demonstrated good agreement between masked observers, based on the intraclass correlation coefficient.^{19,21,22} Studies have demonstrated the best interreader and intrareader reliability when primary efficacy is assessed by trained and validated raters using standardized digital photographs.²³

Safety of topical application of timolol for IH: In contrast to oral propranolol for which safety data from a completed industry-sponsored trial exists, publications reporting the efficacy of topical timolol have not been subjected to the usual stringency of Phase 1/2/3 clinical trials. In addition, these studies have been relatively small in size and short in duration, with no pharmacokinetic data and little to no prospective safety monitoring; therefore, rare adverse events (AEs) may have been missed.

In a prospective study of 124 infants, parents reported no AEs related to study drug administration,

although investigators did not formally monitor bradycardia or hypotension.¹⁸ In the retrospective analysis of 73 infants, parents reported sleep disturbance in one subject, but investigators reported no other AEs in the cohort.¹⁹ In the prospective trial of 41 young infants, only 19 of whom were treated, investigators monitored heart rate and blood pressure at specified intervals until the end of the study.²⁰ There were no significant differences in heart rate or blood pressure between the treatment and observation groups.²⁰

In contrast to the few documented AEs in the above studies, investigators documented episodic bradycardia in 4 of 22 infants who received Holter monitoring concomitant with timolol therapy for IH.²⁴ Two of these infants with clinically significant bradycardia had weights <2500 g at the initiation of therapy, both were <40 weeks postmenstrual age (PMA) at drug initiation, and both were receiving a timolol dose higher than most of the cohort.²⁴ In a case report of an infant treated with ophthalmic timolol and anti-glaucoma medications, the infant developed altered mental status, hypotonia, hypothermia, bradycardia, apnea, hypotension, and bronch- obstruction, and required intensive care.²⁵ A second case report documented apneic spells in a 2-week-old premature infant who was receiving timolol therapy for glaucoma.²⁶ Apneic spells ceased after discontinuation of timolol.²⁶ In the randomized trial that supported use of intraocular timolol maleate gel-forming solution (GFS) in children with glaucoma, 3 of 72 subjects (4%) developed bradycardia or hypotension.²⁷

Pharmacokinetics of topical application of timolol for IH: Information regarding the PK of topical timolol in children is limited. Studies in adults with intraocular application have indicated systemic absorption of up to 80% of each drop of 0.5% timolol solution.²⁸ In a limited PK study (5 pediatric subjects) of intraocular application of 0.5% timolol solution, plasma timolol concentrations ranged from 3.5 ng/mL in a 5-year-old to 34 ng/mL in a 3-week-old.²⁹ Although the GFS form of timolol is thought to have lower systemic absorption compared to the solution, the likelihood of transcutaneous absorption is potentially increased when timolol is applied to the highly vascularized or ulcerated tissue of IH, or in the presence of occlusion (e.g., diaper hemangiomas).¹² Moreover, compromised barrier function of preterm infant skin and smaller volume of distribution relative to adults may lead to increased systemic absorption when compared to adults.¹² Previous investigators measured plasma concentrations of timolol 30 minutes after applying timolol solution to occluded skin over IH after treatment with fractionated CO₂ laser.³⁰ Timolol concentrations were below the limit of detection (20 pg/mL) in all 9 infants. An additional small study demonstrated absorption in all patients sampled (average of 0.18 ng/dL), but the biologic significance of this is unknown.³¹

Preliminary data on safety and outcomes of infants treated with topical timolol: The Hemangioma Investigator Group (HIG) conducted a retrospective, multicenter cohort study of topical timolol (applied directly to the hemangioma) solution for IH.³² This study included 738 infants from 9 pediatric dermatology and vascular anomalies centers, thereby demonstrating the wide off-label use of topical timolol for IH. The majority of infants were prescribed timolol in the outpatient setting and none of these received prolonged monitoring. During the active growth phase (0-3 months of age) 51% of infants showed improvement after 3 months of therapy and 82% after 6-9 months of therapy. AEs were rare, occurring in 3.4% of infants and there were no serious adverse events (SAEs).³² There were no serious cardiovascular adverse events.

Univariate and multivariate mixed-effects models showed that only initial IH thickness significantly predicted early improvement in size ($p = 0.0003$) and color ($p = 0.0001$ with IH <1 mm responding more quickly than IH 1-3 mm or >3 mm). The difference in response lost significance with longer duration of treatment, which may reflect natural involution of thicker lesions. While rebound growth with discontinuation of propranolol is well-recognized, optimal treatment duration for topical therapy to prevent rebound upon discontinuation has not been determined

Preliminary data collection on pharmacokinetics of topical timolol: Through the PTN study entitled “Pharmacokinetics of Understudied Drugs Administered to Children Per Standard of Care (NICHD-2011-POP01),” PK evaluation of topical timolol in premature infants with IH is ongoing. Preliminary serum levels in our PTN sponsored study range from 0.03-66.4 ng/ml with a median of 1 (standard deviation 13.0) ng/ml. None of the infants in this cohort had signs or symptoms of beta blockade or adverse events from timolol.

Timolol clinical pharmacology and product label: Timolol maleate is a nonselective β -adrenergic receptor inhibitor formulated as a 0.25% and 0.5% solution, or GFS for ophthalmic administration. Timolol maleate was approved in 2007 for ophthalmic use for children <6 years of age with glaucoma. Safety and intraocular pressure-lowering effect of timolol maleate GFS 0.25% and 0.5% have been demonstrated in children in a 3-month, multicenter, double-masked, active-controlled trial. This trial included 107 subjects 1 week to <6 years of age who received 1 intraocular drop of either timolol GFS 0.25% or 0.5% once daily.²⁷ PK of timolol GFS was not assessed in this trial.²⁷

According to the product label, contraindications for intraocular inoculation of timolol include: bronchial asthma (or history of), severe chronic obstructive pulmonary disease, sinus bradycardia, second- or third degree atrioventricular block, overt cardiac failure, cardiogenic shock, and hypersensitivity to any component of the product.³³ These contraindications mimic those of other oral beta blockers in children and adults.

2.2 Scientific Rationale

Given the perceived safety of topical application of beta blockers for IH, continued off-label use is expected. Specifically, we predict a precipitous and wide-spread adoption of topical timolol (applied directly to the IH) for treatment of IH by primary care providers over the next 2-5 years. This phenomenon will expose many more infants to this drug. For example, when comparing the incidence of IH (1-4/100) to that of infantile glaucoma for which timolol is FDA approved (1/50,000), 80 times more infants will receive timolol for IH compared to glaucoma, even if only 10% of infants with IH receive beta blocker therapy. Given the likelihood for increased population exposure to topical timolol, and limited existing data about the efficacy, safety, and PK of different timolol formulations, the study of 0.25% and 0.5% topical timolol in a randomized, masked fashion represents an urgent public health need.

2.3 Potential Risks and Benefits

2.3.1 Potential Risks

2.3.1.1 Risks of Blood Drawing

There are small risks to blood sampling, usually some pain/discomfort with the blood stick and blood loss. Every effort will be made to avoid additional (to standard of care) sticks for this study and will time clinical blood draws to coincide with timed samples, using existing intravenous lines when possible.

2.3.1.2 Risks of topical timolol therapy

Transcutaneous absorption of topical timolol solution has not been extensively studied in adults or children. Application of topical timolol to highly vascularized or ulcerated tissue of infantile hemangiomas or under occlusion (e.g. diaper hemangiomas) may increase transcutaneous absorption, and pose a greater risk of adverse events associated with systemic beta-blockers. Effects of systemic beta blockade include bronchial hyperreactivity, hypotension, bradycardia, hypoglycemia, sleep disturbance, hypothermia, and changes in extremity color or temperature e.g., coldness. Infants with known baseline risk factors for bradycardia, hypoglycemia, or bronchial hyperreactivity will be excluded from enrollment according to the protocol's predefined

criteria. More specific to the topical application of timolol, irritation or dermatitis may occur.

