5 STUDY POPULATION

5.1 Selection of the Study Population

Young infants with superficial small hemangiomas in the proliferative phase and who have been identified by their treating physician as needing topical treatment with timolol maleate GFS will be considered for the study. For infants with more than one lesion, a target lesion (a lesion that will require treatment with study drug) will be identified. The infants will be administered study drug only on that lesion. Infants who are eligible for the study based on inclusion and exclusion criteria but whose parents decline treatment with timolol will be included in the non-intervention (control group) in the study.

The majority of recruitment is anticipated to be from outpatient pediatric dermatology clinics, but additional recruitment may occur from inpatient units including the newborn nursery and neonatal intensive care units.

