5.2.2 Exclusion Criteria

1. History of previous treatment with any pharmacologic or laser therapy for IH
2. Ongoing therapy with an oral beta blocker or oral corticosteroid (e.g., cardiac arrhythmia, adrenal insufficiency, upper airway obstruction, tetralogy of fallot, hypertension, reactive airways disease)
3. IH that requires systemic therapy (defined by dynamic complication scale >3)
4. Infants with more than one hemangioma that requires therapy
5. IH of the non-keratinized mucosa
6. Hemodynamically significant cardiovascular disease, as determined by the investigator
7. Known allergy to beta blockers or vehicle
8. Heart rate <100 beats per minute at screening visit
9. Known prenatal or postnatal diagnosis of 2nd/3rd degree atrioventricular block
10. History of reactive airway disease (RAD)
11. Any condition which would make the participant, in the opinion of the investigator, unsuitable for the study

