⁸OUTPATIENT: When possible the participant should remain in clinic for 2 hours after the first application of timolol in order to monitor for heart rate and BP at 1 hour (+/-15 mins) and 2 hours (+/- 15 mins) after first application. The site PI must also monitor for signs of bradycardia, bronchospasm and hypoglycemia.

INPATIENT: All inpatients will be monitored for the first 24 hours for any signs of bradycardia or any other SAEs of special interest. Hospital staff must also monitor BP and HR 1 and 2 hours after the first administration of timolol.

⁹If performed per local standard of care (SOC)

¹⁰ Blood Pressure Measurement should include systolic and diastolic measurements

*All visits (except for Day 7 post 180 days study period or early withdrawal) can occur within a 5 day window (± 5 days). Day 7 post 180 day study period or early withdrawal must occur within a +5 day window (+5 days).

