6.3 Enrollment/Baseline

Research staff will obtain informed consent from the parent/guardian for all participants who satisfy eligibility criteria.

Once the informed consent has been obtained the following information will be recorded in the CRF:

1. Infant demographics, including birth weight and gestational age at birth and postnatal age.
2. Medical history (birth history and cardiac or pulmonary diagnoses)
3. Physical examination, including weight, height/length, baseline blood pressure, heart rate. Note, at the Baseline Visit, blood pressure* and heart rate must be at 1 hour and 2 hours after the first application of timolol.
4. Photographs and measurements of the IH. Collection of data on the clinical characteristics and measurement of width and thickness of the target hemangioma.
5. Adverse events following initial study-specific procedure (see Table 6-1)
6. Hemangioma Dynamic Complication Scale
7. Parental Hemangioma Quality of Life (QoL) screen
8. Concomitant Medications

* The preferred method of blood pressure collection is auscultation (i.e. manual), however, blood pressure may be collected via machine. Whichever method is used at visit #01 (baseline) should be used at all subsequent visits. Blood pressure measurements should include systolic and diastolic pressure measurements.

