8.1.4 Identification of Events and Timeframe for Reporting

Pre-existing conditions will not be considered as adverse events. New events that occur or pre-existing conditions that worsen in terms of frequency or intensity will be reported as adverse events.

All reportable events as defined above, determined to be an AE based on physical examination, laboratory findings, or other means, will be reported in the electronic case report form (e-CRF). The investigator will provide the date of onset and resolution, intensity, action(s) taken, changes in study drug dosing, relationship to study drug, and outcome.

Any event excluding adverse events of special interest beginning more than 7 days after the last dose of study drug or last study procedure will not be reported. For participants in the treatment arm adverse events of special interest only will be reviewed and reported at 90 days after the last dose of study drug.

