The IND sponsor or designee will provide the investigator, in writing, any new information that bears significantly on the infants' risk to receive the investigational product. This new information will be communicated by the investigator to infants' parent(s)/legal guardian who have consented for their infant to participate in the trial in accordance with IRB requirements. The informed consent document will be updated, and infants' legal guardians will be re-consented, if necessary.

Site staff may employ IRB-approved recruitment efforts prior to informed consent; however, before any protocol-specific procedures are performed to determine protocol eligibility, informed consent must be obtained and properly executed. The investigator will choose infants in accordance with the eligibility criteria detailed previously. To prevent bias, the investigator will not exercise selectivity.

By providing consent, the infant's parent/legal guardian agrees that the infant will complete all evaluations required by the trial, unless the infant's parent/legal guardian withdraws the infant voluntarily or the infant is withdrawn from the trial for any reason.

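### Section 2.3.1.2 says infants with known hypoglycemia risk factors are excluded under predefined criteria, but neither eligibility list contains such a criterion

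*Combined protocol and SAP*

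**What the plan says.** Section 2.3.1.2 lists hypoglycemia among the effects of systemic beta blockade and then states: "Infants with known baseline risk factors for bradycardia, hypoglycemia, or bronchial hyperreactivity will be excluded from enrollment". The sentence goes on to attribute this to the protocol's own predefined criteria.

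Those criteria are in section 5.2.2, and the synopsis repeats them. Each list has 11 exclusions with the same content, with items 4 and 5 in reverse order. Two entries come near hypoglycemia risk:

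- Exclusion 2: "Ongoing therapy with an oral beta blocker or oral corticosteroid (e.g., cardiac arrhythmia, adrenal insufficiency", followed by further example conditions.
- Exclusion 11: "Any condition which would make the participant, in the opinion of the investigator, unsuitable for the study".

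Section 6.3, item 2, sets the baseline history: "Medical history (birth history and cardiac or pulmonary diagnoses".

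Elsewhere the protocol deals with hypoglycemia at or after dosing. Section 6.4.1 has parents apply the drug after feeds to avoid it. Note 8 to Table 6-1 says of outpatients: "The site PI must also monitor for signs of bradycardia, bronchospasm and hypoglycemia". Section 6.7 calls for glucose testing on clinical indication, and section 8.1.2 lists hypoglycemia as an adverse event of special interest.

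**The concern.** The risk section is where ethics boards and sites look to see how a known hazard is controlled. For this hazard it reports a protection at entry. If the entry rules do not contain that protection, what readers are told differs from what a site applying the list will do.

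What is at stake is which infants are dosed. The population is 0 to 84 days old. Most recruitment is expected from outpatient clinics, but section 5.1 adds that "additional recruitment may occur from inpatient units including the newborn nursery and neonatal intensive care units". Section 2.3.1.2 itself warns that absorption may rise when the drug is put on highly vascular, ulcerated or occluded lesions. An infant with a known tendency to low glucose is one the authors say they meant to keep out, and the list does not tell a site to do so.

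**Working it through.** The plan gives no figure on this point, so the check is a comparison of texts. The inputs are the sentence in 2.3.1.2, the exclusions in 5.2.2 and the synopsis, the inclusion criteria, and the baseline list in 6.3. Both eligibility lists and section 6.3 are present in full, so missing or blacked-out text does not explain the result.

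Step 1. Take each risk named in 2.3.1.2 and look for an exclusion that addresses it in substance, whether or not it uses the same word.

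| Risk named in 2.3.1.2 | Matching exclusion in 5.2.2 and the synopsis |
|---|---|
| Bradycardia | No. 8 (heart rate under 100 at screening) and no. 9 (2nd or 3rd degree atrioventricular block) |
| Bronchial hyperreactivity | No. 10 (history of reactive airway disease) |
| Hypoglycemia | None of its own; no. 2 in part; no. 11 by judgement |

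So 2 of the 3 risks have a dedicated criterion, and hypoglycemia has 0 of 11. The inclusion criteria do not mention glucose or hypoglycemia either.

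Step 2. See how far exclusion 2 reaches. Its trigger is current oral therapy. It removes an infant on an oral beta blocker, which 2.3.1.2 itself links to hypoglycemia, and an infant whose adrenal insufficiency is treated with an oral corticosteroid. It does not remove an infant with a known hypoglycemia risk who takes neither drug. Adrenal insufficiency appears only as an example of a reason for the therapy.

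Step 3. See how far exclusion 11 reaches. It permits exclusion of such an infant but does not require it, and it names no condition. A criterion that rests on the investigator's view is not a predefined hypoglycemia criterion, and sites may apply it differently.

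Step 4. Ask whether the information would be collected. The 6.3 history covers birth history and cardiac or pulmonary diagnoses. Birth history could bring up early hypoglycemia by chance, but no metabolic or glucose item is requested. Section 6.7 provides testing on clinical indication, not a screening glucose.

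Step 5. Put these together. An infant with a known hypoglycemia risk, on neither drug in exclusion 2 and not judged unsuitable under exclusion 11, meets section 5.2 and falls outside what 2.3.1.2 says will be enrolled.

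**The case against.** The strongest reply is that this is a loosely worded sentence and not a missing safeguard. Exclusions 6 to 10 closely track the label contraindications summarised in section 2.1, and hypoglycemia is not among those listed there. The topical and ophthalmic safety experience described in that section does not mention hypoglycemia. Exclusion 2 does remove some infants at risk. An investigator who has read 2.3.1.2 can use exclusion 11 for the rest. The safeguards after enrolment are real: dosing after feeds, 24-hour monitoring of inpatients, a 2-hour stay requested of treated outpatients, glucose testing on clinical indication, and a pause for review at two serious adverse reactions (section 8.5).

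Much of this stands. It supports correcting the sentence as a legitimate alternative repair, and it means hypoglycemia is not neglected in the trial. It does not remove the mismatch: the safeguards act at or after dosing, and 2.3.1.2 speaks of exclusion before it.

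Three stronger readings are tempting, and the documents support none of them.

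- A reader might infer that section 12 obliges sites to enrol these infants, because it says "The investigator will choose infants in accordance with the eligibility criteria detailed previously" and rules out selectivity. The listed criteria include exclusion 11, so section 12 does not stop a site from using it.
- A reader might infer that hypoglycemia events could not be classified, because section 8.1.4 says "Pre-existing conditions will not be considered as adverse events" and no glucose history is required. But the same section reports worsening of pre-existing conditions and asks for onset dates. Section 8.1.2 sets a fixed glucose threshold for this event and does not confine it to new cases. The case report form and manual of procedures, which could ask for more history, are not available here. The effect is not shown.
- A reader might try to estimate how many at-risk infants would enter. The documents give no frequency of known hypoglycemia risk among eligible infants, and exclusions 2 and 11 would remove an unknown share, so any such number would be invented.

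**Conclusion.** The point holds as an internal inconsistency that affects safety eligibility. Section 2.3.1.2 reports an exclusion under predefined criteria that sections 5.2.2 and the synopsis do not contain. Coverage is partial through exclusion 2 and discretionary through exclusion 11, and the 6.3 history does not ask for the information.

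Its size is one of three named risks without its own criterion. The conclusion rests on reading predefined criteria to mean criteria that identify the risk without relying on an individual investigator's opinion. If exclusion 11 were accepted as meeting that description, what would remain is uneven use between sites and a history that does not prompt the question.

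The finding does not show that any infant would be harmed. Sample size, power and the efficacy analysis are unaffected.

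**What to change.** Preferred change, if the exclusion is intended:

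1. Add to section 5.2.2 and the synopsis an exclusion for known hypoglycemia or a known diagnosed condition predisposing to hypoglycemia. The clinical team should list the qualifying conditions in the criterion itself so that sites apply it alike. They should also say whether resolved early hypoglycemia counts, and whether prematurity alone does, since section 4.1 expects 10% of enrolled infants to be preterm.
2. Add metabolic/glucose history to item 2 of the baseline list in section 6.3.

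Alternative, if the exclusion is not intended: remove hypoglycemia from the sentence in 2.3.1.2 and state there that this risk is managed by dosing after feeds and by monitoring.

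Either route is one short amendment with no new test or visit. The first costs a few more exclusions, provided the list is kept to diagnosed conditions. The second costs nothing in recruitment, but it tells ethics boards and sites plainly that such infants may be enrolled.
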